9.10.3 Vital Signs

Vital signs will include blood pressure, pulse, and body temperature and will be taken after the patient has been resting for at least 5 minutes during screening, at study visits during the Treatment Phase, at the Treatment Discontinuation Visit and the 28-Day Follow-up Visit.

9.10.4 12-Lead Electrocardiogram

For all patients, 12-lead ECGs will be performed at the following times:

- Screening (within 28 days prior to enrollment)
- Treatment Discontinuation Visit

The following will be measured or calculated: heart rate, PR, QRS, QT, QTc, and rhythm. The investigator or qualified designee will review the ECGs locally and assess the results as normal or abnormal (clinically significant or not clinically significant).

If it is clinically indicated, ECGs can be performed at other times during the study.

9.10.5 Body Weight and Height

Height will be measured during the screening visit only. Weight will be measured per institutional guidelines during screening, during treatment at each study visit, at the Treatment Discontinuation Visit, and the 28-Day Follow-up visit.

9.10.6 Physical Examinations

Physical examinations will include an assessment of all the major body systems. Complete physical examinations will be performed during screening and at treatment discontinuation. Physical examinations at study visits during the Treatment Phase and 28-Day Follow-up Visit will be limited as appropriate.

9.10.7 ECOG Performance Status

ECOG performance status ([Appendix 3](#)) will be assessed during screening, at study visits during the Treatment Phase, at the Treatment Discontinuation Visit and 28-Day Follow-up Visit. The ECOG performance status should be assessed by the same study personnel at each visit, if

possible. For eligibility purposes, patients with borderline ECOG performance status should be considered carefully to avoid enrolling patients who may have significant impairment.

9.11 Biomarker Analysis – FFPE Tumor Tissue

An optional tumor biopsy obtained between the time of disease progression/treatment discontinuation and the start of the next treatment will be obtained from consenting patients. The molecular profile of the progression biopsy will be compared with that from pretreatment primary or metastatic tumor tissue to identify mechanisms of resistance to rucaparib. Patients must provide additional consent for the optional tumor tissue biopsy sample. New lesions or lesions that are growing should be prioritized for the optional biopsy. If possible, collect the lesion responsible for progression. Detailed sample handling instructions are located in the Pathology Charter.

9.12 Biomarker Analysis – Blood

Blood samples for plasma ctDNA will be collected during Pre-Screening (for deleterious BRCA, ATM, or other HRR gene mutation assessment), Screening, before dosing on Study Day 1, every 28 days thereafter, and at treatment discontinuation from all patients entered in the study. Blood samples for pharmacogenomics analyses will be collected on Study Day 1 from all patients entered in the study. Genomic DNA will be extracted from the cellular portion of this blood sample and analyzed to determine whether the deleterious BRCA/ATM/other HRR gene mutation is germline or somatic prior to final data analysis. Because the germline analysis will be done near the end of the study, there are no plans to share these results with the investigator. However, if an actionable mutation, as defined by the American College of Medical Genetics and Genomics (<https://www.ncbi.nlm.nih.gov/clinvar/docs/acmg/>), is revealed that was not detected in tumor or plasma, these incidental finding will be made available to the investigator provided the results are generated from a Clinical Laboratory Improvement Amendments (CLIA)-certified laboratory. Sample collection details will be provided in a Laboratory Manual.

9.13 Pharmacokinetics Evaluation

Plasma samples are to be collected for trough level PK analysis of rucaparib 1 hour before the morning dose on Study Day 29, Day 57, Day 85, and Day 113. If the start of the next dose is postponed or suspended, the PK sample should be collected as close to 12 hours after the previous dose as possible. Refer to the Laboratory Manual for sample collection details for PK samples.

9.14 Patient Reported Outcomes (Health and Quality of Life Questionnaires)

Patient reported outcomes utilizing the BPI-SF, ([Appendix 6](#)), FACT-P ([Appendix 7](#)), EQ-5D-5L ([Appendix 8](#)), and analgesic drug score instruments ([Appendix 9](#)) will be assessed during screening, Study Day 1 and every 28 days thereafter, at the Treatment Discontinuation Visit, at the 28-Day Follow-up Visit, and if applicable, during long term follow-up. The analgesic drug score will be recorded according to the WHO's analgesic ladder: 0 for no analgesic, 1 for nonopioids, 2 for opioids for moderate pain, and 3 for opioids for severe pain.⁴⁶

Patients should complete the instruments before any other scheduled study procedures are performed and dosing occurs (if applicable). For patients who discontinued treatment prior to radiologic disease progression, PRO assessments should be collected until subsequent radiologic disease progression was documented.

10 ADVERSE EVENT MANAGEMENT

10.1 Definition of an Adverse Event

An AE is defined as any untoward medical occurrence in a patient administered a medicinal product that does not necessarily have a causal relationship with this treatment. An AE can, therefore, be any unfavorable and unintended sign (including an abnormal laboratory finding), symptom, or disease temporally associated with the use of an investigational product, whether or not related to the investigational medicinal product. This includes an exacerbation of pre-existing conditions or events, intercurrent illnesses, or drug interaction that is not recorded elsewhere on the eCRF - under specific efficacy assessments. Anticipated fluctuations of pre-existing conditions, including the disease under study, that do not represent a clinically significant exacerbation or worsening are not considered AEs.

It is the responsibility of the investigator to monitor all AEs that occur during the study. AEs should be elicited by asking the patient a non-leading question (eg, “Have you experienced any new or changed symptoms since we last asked/since your last visit?”). The existence of an AE may be concluded from a spontaneous report of the patient; from the physical examination; or from special tests such as the ECG, laboratory assessments, or other study-specified procedure (source of AE). Symptoms reported spontaneously by the patient during the physical examination would also qualify as an AE (and hence documented on the AE eCRF, not on the physical examination eCRF, which is reserved for physical signs or findings).

10.2 Definition of a Serious Adverse Event

An SAE is any untoward medical occurrence that occurs at any dose (or, occurs after informed consent is given and prior to dosing if the SAE is related to a study procedure) that:

- Results in death. Any event resulting in death during the reporting period (from date of first dose of rucaparib through 28 days after last dose) must be treated as an SAE and reported as such. An event related to a study procedure that occurs after informed consent, but prior to dosing that results in death must also be reported as an SAE. This excludes death due to progression of patient’s underlying cancer. (refer [Section 10.4](#));
- Is life-threatening (patient is at immediate risk of death from the event as it occurred);
- Requires in-patient hospitalization (formal admission to a hospital for medical reasons) or prolongation of existing hospitalization;
- Results in persistent or significant disability/ incapacity;
- Results in a congenital anomaly or birth defect;
- Important medical events that may not result in death, are not life-threatening, or do not require hospitalization may be considered SAEs when, based on appropriate medical judgment, they may jeopardize the patient and may require medical or surgical intervention to prevent one of the outcomes listed in this definition. Examples of such events include allergic bronchospasm requiring intensive treatment in an emergency room or at home or the development of drug dependency or drug abuse.

10.3 Definition of an Adverse Event of Special Interest

AESIs (serious or nonserious) are defined as AEs of scientific and medical concern specific to the sponsor's product or program, for which ongoing monitoring and rapid communication by the investigator to the sponsor can be appropriate. Such an event might warrant further investigation in order to characterize and understand it. Depending on the nature of the event, rapid communication by the trial sponsor to other parties (eg, regulators) might also be warranted.

Details on the sponsor's currently agreed list of AESIs for rucaparib can be found in the current rucaparib IB. These AESIs are to be reported to the sponsor **within 24 hours** of knowledge of the event (see [Section 10.7](#) for reporting instructions).

10.4 Events or Outcomes Not Qualifying as Serious Adverse Events

The following are not considered SAEs and therefore do not need to be reported as such:

- Preplanned or elective hospitalization including social and/ or convenience situations (eg, respite care);
- Hospital visits of less than 24 hours duration (eg, patient presents to the emergency room, but is not admitted to a ward);
- Overdose of either Clovis study drug or concomitant medication unless associated with an SAE. However, the event should still be captured as a nonserious AE on the appropriate eCRF page;
- Events of progression of the patient's underlying cancer as well as events clearly related to progression of the patient's cancer (signs and symptoms of progression) and progression of disease leading to death should not be reported as an AE or SAE. This section excludes other SAEs with fatal outcome;
- Events that meet the SAE criteria (as outlined in [Section 10.2](#)) and occur after informed consent but before the first dose of study drug, which are considered unrelated to protocol-mandated procedures.

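### Protocol Section 10.4 excludes hospital visits under 24 hours from SAE reporting without limiting the exclusion to the hospitalization criterion, so some events serious under Section 10.2 could be classified as nonserious

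*Protocol*

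**What the plan says.** Under Protocol Section 10.2 an event is serious if it meets any one of several criteria. Three matter here:

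- Hospitalization: "Requires in-patient hospitalization (formal admission to a hospital for medical reasons) or prolongation of existing hospitalization". No minimum stay is given.
- Danger to life: "Is life-threatening (patient is at immediate risk of death from the event as it occurred". Neither the place of treatment nor its length enters.
- Medical importance: "Important medical events that may not result in death, are not life-threatening, or do not require hospitalization may be considered SAEs", on the basis of medical judgment. The section illustrates this: "Examples of such events include allergic bronchospasm requiring intensive treatment in an emergency room or at home".

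Section 10.4 introduces its exclusions with "The following are not considered SAEs and therefore do not need to be reported as such". The second of its five bullets reads "Hospital visits of less than 24 hours duration (eg, patient presents to the emergency room, but is not admitted to a ward" and carries no condition. The overdose bullet directly after it does: "Overdose of either Clovis study drug or concomitant medication unless associated with an SAE". The last bullet opens with "Events that meet the SAE criteria", refers back to 10.2, and removes events before first dose that are unrelated to protocol-mandated procedures.

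Section 10.7 sets the consequences. Every AE from first dose to 28 days after last dose goes on the AE eCRF and is evaluated for causality, severity and seriousness. SAEs and AESIs in that period go to the sponsor within 24 hours. After the 28-Day Follow-up Visit, only SAEs potentially related to rucaparib, and MDS or AML, are reported. In Pre-Screening and Screening, only serious events related to a protocol-mandated procedure are reported.

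**The concern.** Section 10.4 is the list a site would consult when deciding that something is not an SAE. Its hospital-visit bullet and the important-medical-event criterion in 10.2 both use the emergency room as their example, and they point the site in opposite directions. One says that an event treated there may be serious; the other says that a short visit there is not an SAE.

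What is at stake is the serious label. That label triggers the 24-hour report (10.7), the sponsor's assessment for reporting serious and unexpected events to regulators (10.10), and entry in the Serious TEAE tables (Protocol 11.6.1, SAP 12.1). In the periods when only SAEs are reported, it also decides whether the event is reported as an adverse event at all.

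**Working it through.** No arithmetic applies, and the plan gives no figure to reproduce. The check sets the two sections side by side and then follows the reporting route.

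**Step 1. Four cases under each section.** The literal reading takes the 10.4 bullet as it stands. The narrow reading takes it as clarifying only what counts as hospitalization.

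| Case | 10.2 | 10.4, literal | 10.4, narrow |
|---|---|---|---|
| Minor event, emergency-room visit, not admitted | Not serious | Not an SAE | Not an SAE |
| Life-threatening event resolved in under 24 hours, not admitted | Serious | Not an SAE | Serious |
| Bronchospasm needing intensive emergency-room treatment, released the same day | May be serious, by judgment | Not an SAE | May be serious, by judgment |
| Formal admission for medical reasons lasting 18 hours (illustrative) | Serious | Not an SAE, if a visit includes an admission | Unclear |

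The first case causes no difficulty. The second and third conflict under the literal reading only. The fourth is not fully settled by the narrow reading, because two tests for hospitalization remain: formal admission in 10.2 and a 24-hour duration in 10.4. The non-admitted patient in 10.4 is given as an example, not as a limit.

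**Step 2. Whether 10.4 says which reading applies.** It does not. Its title and opening line concern what is not an SAE, without tying any bullet to a particular criterion. Three of the other four bullets (overdose, progression, events before first dose) state how they relate to seriousness; the hospital-visit bullet does not.

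**Step 3. What a misclassified event loses, by period.**

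- *First dose to 28 days after last dose.* The event stays on the AE eCRF and in the general TEAE tables, and in the Grade 3 or higher tables if its grade qualifies. It loses the 24-hour SAE report, the expedited-report assessment and its place in the Serious TEAE tables.
- *After the 28-Day Follow-up Visit.* MDS and AML apart, only related SAEs are reported. A related event called nonserious has no reporting route.
- *Pre-Screening and Screening.* Only procedure-related SAEs are reported. A procedure-related event called nonserious would at most reach the Medical History eCRF under 9.7.1. Section 10.7 words the Medical History rule so that procedure-related events fall outside it. Pre-Screening asks for a new metastatic biopsy where feasible (5.1.1, 9.3). A serious biopsy complication handled within a day in the emergency room is therefore exposed, to the extent that the biopsy counts as protocol-mandated.

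**Step 4. Events protected whatever 10.4 says.** The listed pneumonitis-type AESIs go within 24 hours on the SAE form irrespective of severity (10.7), up to the 28-Day Follow-up Visit. Potential drug-induced liver injury meeting the defined criteria must be reported as an SAE (10.9).

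**The case against.** The strongest reply is that the narrow reading is what was meant. The bullet names visits, not events, and its example is a patient who was not admitted; 10.2 would not call that hospitalization either. Where 10.4 does remove events that satisfy 10.2, in its last bullet, it says so. The elective-hospitalization bullet also lacks an exception, yet it would be hard to read it as excluding a life-threatening event during an elective stay. An overdose is itself an event and so needs an exception; a visit is only a setting. Finally, 10.7 requires a seriousness evaluation for every AE.

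Much of this stands. The narrow reading is plausible, and the contrast with the overdose bullet is suggestive rather than decisive. Still, the narrow reading is nowhere stated, and a seriousness evaluation made with 10.2 and 10.4 in hand inherits the conflict between them. A site could misread the bullet in good faith.

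A reader might go further and infer that serious events managed in the emergency room would go unreported. The documents do not support that: on-treatment events remain recorded as AEs, and some have their own reporting routes. Nor do they support the inference that all such events are SAEs under 10.2 and none under 10.4, because important medical events are left to judgment and the exclusion of all of them assumes the literal reading.

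Two further inferences also fail. Section 13.6 gives the DMC safety data and describes no feed limited to serious events, so a loss to the DMC is not shown. The single-arm design is not what hides any shortfall either, since the same rule would apply in both arms of a controlled trial.

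**Conclusion.** The concern holds as a conflict of wording with a possible reporting consequence. Read literally, the bullet excludes events that 10.2 makes serious, or allows to be judged serious. The exposed events are life-threatening or medically important events managed in under 24 hours and, less certainly, formal admissions shorter than that.

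The consequence is a risk of misclassification, not a demonstrated loss. It rests on the assumption that at least some sites apply 10.4 as written. Its size cannot be stated, because the documents give neither the number of short hospital visits nor the share involving an event serious on another criterion. Counts in the Serious TEAE tables could be too low. Sample size, error rates and the efficacy analyses are untouched. The point is worth correcting because the correction is small and the affected route is expedited safety reporting.

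**What to change.** Reconcile 10.4 with 10.2 by rewording the bullet along these lines: *Hospital or emergency-room visits without formal admission, unless the event meets any other seriousness criterion in Section 10.2.* This removes a 24-hour threshold that 10.2 does not contain, leaves formal admission as the single test of hospitalization, and keeps the other criteria in force. It sets no clinical rule.

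The cost is one reworded bullet, handled as a protocol amendment under 13.8, and a notice to sites. There may be slightly more SAE reports. No change to the SAP is needed.

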10.5 Clinical Laboratory Assessments as Adverse Events and Serious Adverse Events

It is the responsibility of the investigator to assess the clinical significance of all abnormal values as defined by the list of reference ranges from the local laboratory. In some cases, significant changes in lab values within the normal range will require similar judgment.

An abnormal laboratory value that is not already associated with an AE is to be recorded as an AE only if any 1 of the following criteria is met:

- an action on rucaparib treatment is made as a result of the abnormality

- intervention for management of the abnormality is required
- at the discretion of the investigator should the abnormality be deemed clinically significant

10.6 Pregnancy or Drug Exposure During Pregnancy

A pregnancy is not considered to be an AE or SAE; however, any pregnancy occurring in a partner of a study patient during study participation or within 3 months of last dosing must be reported to the sponsor using the Pregnancy Report Form within the same timelines as an SAE.

A pregnancy will be followed through to outcome. Once the outcome of the pregnancy is known, the Pregnancy Outcome Report Form is to be completed and reported to the Sponsor.

AEs, SAEs, or AESIs that occur during pregnancy will be assessed and processed according to the AE or SAE/AESI processes using the appropriate AE or SAE/AESI forms.

10.7 Recording of Adverse Events, Serious Adverse Events, and Adverse Events of Special Interest

Events that occur after signing of informed consent but prior to initiation of rucaparib, unless due to a protocol-mandated procedure, are to be recorded on the Medical History eCRF; however, events are to be reported as SAEs if serious and related to a protocol-mandated procedure during the Pre-Screening Phase or Screening Phase.

Any AE that occurs after first dose of rucaparib through 28 days after receiving the last dose of rucaparib will be recorded on the AE eCRF.

Report any AE of pneumonitis, or any of the following AEs, irrespective of causality assessment and severity, as an AESI within 24 hours using the study Serious Adverse Event Form:

- Pneumonitis
- Interstitial lung disease
- Pulmonary fibrosis
- Acute interstitial pneumonitis
- Alveolitis necrotizing
- Alveolitis
- Hypersensitivity pneumonitis
- Organizing pneumonia

After the 28-day Follow-up Visit, only SAEs assessed as potentially related to rucaparib should be reported per Clovis PV requirements and captured in the Clovis PV database. This includes serious reports of pneumonitis or associated events, if considered to be related to study drug.

After the 28-day Follow-up Visit, AESIs of MDS and AML, irrespective of causality, should be reported per Clovis PV requirements and captured in the Clovis PV database.

- AESIs of pneumonitis or associated events should only be reported up to, but not beyond, the 28-day Follow-up Visit (ie, 28-days after the last dose of rucaparib).

Information on the follow-up of AEs, SAEs, and AESIs is provided in [Section 10.8](#).

In order to avoid vague, ambiguous, or colloquial expressions, the AE should be recorded in standard medical terminology rather than the patient's own words. Whenever possible, the investigator should combine signs and symptoms that constitute a single disease entity or syndrome into a final diagnosis, if appropriate. For example, fever, cough, and shortness of breath may be reported as pneumonia, if that is a reasonable diagnosis.

Each AE is to be evaluated for causal relationship to rucaparib, severity, and seriousness. The action taken and the outcome must also be recorded.

SAEs and AESIs that occur during the study or within 28 days after receiving the last dose of rucaparib, whether or not related to rucaparib, must be reported immediately (ie, **within 24 hours** of knowledge of the event or additional information for a previously-reported event) to the sponsor/ SAE designee. The contact information for reporting of SAEs/AESIs can be found on the SAE/AESI Reporting Form.

10.7.1 Onset Date of Adverse Events

The onset date is the date that the event or the signs/symptoms attributed to the event started.

10.7.2 Resolution Date of Adverse Events

The resolution date is the date that the event or the signs/symptoms attributed to the event resolved or resolved with sequelae or it is the date when the patient has reached a new baseline if the event is not expected to resolve.

10.7.3 Intensity of Adverse Events

The severity of each AE will be graded using the NCI CTCAE, Version 4.03 or higher grading scale (http://evs.nci.nih.gov/ftp1/CTCAE/CTCAE_4.03_2010-06-14_QuickReference_8.5x11.pdf).⁴⁷

Severity is not the same as Serious.

For AEs not covered by NCI CTCAE, the severity will be characterized as mild, moderate, severe, life-threatening, or fatal according to the following definitions:

- Mild events are usually asymptomatic or have mild symptoms with clinical or diagnostic observations only; intervention is not indicated
- Moderate events introduce a low level of inconvenience or concern to the patient, local or noninvasive intervention may be indicated, and may interfere with age-appropriate daily activities

- Severe events are medically significant, but not immediately life-threatening; interrupt the patient’s usual self-care daily activities, disabling, and hospitalization (or prolongation of hospitalization) is indicated
- Life-threatening events require urgent intervention to prevent death; or
- Fatal events are those events that lead to the patient’s death

